11. STATISTICAL METHODS

Statistical analysis will be done by the sponsor or under the authority of the sponsor. A general description of the statistical methods to be used to analyze the efficacy and safety data is outlined below. Specific details will be provided in the Statistical Analysis Plan (SAP).

Descriptive statistics will include counts and proportions for categorical data, and median, mean, interquartile range, and range for continuous data. Graphical data displays may also be used to summarize the data.

Analyses suitable for categorical data (eg, chi-square tests or Cochran-Mantel-Haenszel (CMH) chi-square tests or Fisher's exact test, as appropriate) will be used to compare the proportions of subjects achieving selected endpoints (eg, PPPASI-50). Continuous response parameters will be analyzed using a mixed-model for repeated measures (MMRM) (for repeated measurements) or

an analysis of variance (ANOVA) or covariance (ANCOVA). If the normality assumption is in question, an ANOVA or ANCOVA on the van der Waerden normal scores will be used.

Subject baseline data, demographic and baseline clinical disease characteristics will be summarized. The baseline measurement is defined as the closest measurement taken at or before the time of the Week 0 administration.

11.1. Subject Information

For all subjects who are randomly assigned to study drug, descriptive statistics by the randomized treatment group based on all randomized subjects will be provided for subject dispositions, demographics, baseline disease characteristics, and prior and concomitant medications.

11.2. Sample Size Determination

This study is designed to evaluate the efficacy of CNTO 1959 versus placebo in subjects with palmoplantar pustulosis at Week 16. Palmoplantar Pustulosis Area and Severity Index (PPPASI) total score will be used in this study as the primary variable. A fixed-sequence testing procedure, starting with the high dose group (CNTO 1959 200 mg), will be used to control the overall Type I error rate at the 0.05 level (2-sided) for comparisons of the 2 CNTO 1959 treatment groups with the placebo group.

The sample size was chosen to achieve at least 90% power to detect treatment difference between CNTO 1959 groups and placebo for the primary endpoint at a significance level of 0.05 (2-sided).

The assumptions for the sample size and power calculations came from the results of a phase 2 study in subjects with PPP (CNTO1959PPP2001):

Table 1: Change from baseline in PPPASI score at Week 16 in CNTO1959PPP2001 study

	Placebo	CNTO1959 200 mg
n	24	25
Mean \pm SD	-6.40 \pm 7.545	-10.24 \pm 8.072
LS mean ^a	-5.47	-11.12
LS mean difference (SE) (versus Placebo) ^a	-5.65 (2.061)	
95% CI for difference in LS mean (versus Placebo) ^a	(-9.80, -1.50)	
p-value (versus Placebo) ^a	0.009	

a. Based on ANCOVA with treatment as a factor and baseline PPPASI total score as a covariate.

Since the baseline PPPASI total score in CNTO1959PPP2001 study is deemed unbalanced across the comparison groups due to its exclusion from stratification factors, LS-means should be able to provide fairer comparisons than would comparisons of the raw means and as a result, the assumed treatment effect size is based upon the LS mean difference. Assuming a 5.5 treatment effect for both CNTO 1959 groups and a common standard deviation (SD) of 8.1 in change from baseline in PPPASI score at Week 16, 47 subjects per group will provide statistical power of 90% for comparisons of CNTO 1959 200 mg versus placebo at a significance level of 0.05 (2-sided).

Table 2: Power for a fixed sample size (47 subjects/treatment) at alpha = 0.05 with different assumptions about the change from baseline in PPPASI score at Week 16

Difference	SD	Power
4.5	7.5	82%
	8.1	75%
	8.5	71%
5.0	7.5	89%
	8.1	84%
	8.5	80%
5.5	7.5	94%
	8.1	90%
	8.5	87%

Based on the two sample t-test with equal variances of Query Advisor. Release 7.0.

To account for a larger common standard deviation, assuming a fixed 5.5 difference between groups and a common SD of 10, the required number of patients per group for a 90% power is 75. Meanwhile, an evaluable long-term safety population for CNTO 1959 is considered to have at least 50 patients per group. Therefore, the study design is pre-planned as 50 patients per group but with the option of an adaptive sample size re-estimation with a maximum allowable sample size of 75 patients per group (225 in total).

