This study is designed to evaluate the efficacy of CNTO 1959 versus placebo in subjects with palmoplantar pustulosis at Week 16. PPPASI total score will be used in this study as the primary variable. A fixed-sequence testing procedure, starting with the high dose group (CNTO 1959 200 mg), will be used to control the overall Type I error rate at the 0.05 level (2-sided) for comparisons of the 2 CNTO 1959 treatment groups with the placebo group. The sample size of 50 patients per group was chosen to achieve at least 90% power to detect treatment difference between CNTO 1959 group and placebo for the primary endpoint at a significance level of 0.05 (2-sided).

The assumptions for the sample size and power calculations came from the results of a phase 2 study in subjects with PPP (CNTO1959PPP2001).

Interim Analysis

Since the assumptions used for determining the sample size may or may not be upheld in this study, an interim analysis is planned to re-estimate the sample size and determine whether to stop the study early for futility based on the approach introduced by Mehta and Pocock.¹⁶

This interim analysis will be conducted when approximately 40% of the 150 randomized subjects have completed Week 16 visit or have ended study participation before Week 16 visit. Conditional power and the sample size required for satisfying the 90% conditional power will be calculated by an independent Statistical Support Group (SSG). The IDMC will compare the calculated results with the pre-specified sample size adaptation rules to determine the final sample size for the study. The maximum sample size for the study is capped at 75 patients per group (225 in total).

Efficacy

Primary endpoint of this study is change from baseline in PPPASI total score at Week 16. In the primary efficacy analyses, data from all randomized subjects will be analyzed according to their assigned treatment group. In this primary analysis, the change from baseline in PPPASI total score through Week 16 will be analyzed using an MMRM with treatment (CNTO 1959 high dose, CNTO 1959 low dose, or placebo), smoking status (smoking or non-smoking), week (2, 4, 8, 12, 16), and treatment-by-week interaction as fixed effects and baseline PPPASI score as a covariate. Un-imputed data will be used for

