A fixed-sequence testing procedure will be used to control the overall Type I error rate at the 0.05 level for the primary endpoint. Specifically, the high dose group (i.e., CNTO 1959 200 mg) will first be compared with the placebo group at the 2-sided 0.05 level of significance. Only if this test is positive will the low dose group (i.e., CNTO 1959 100 mg) be compared with the placebo dose group at the 2-sided 0.05 level of significance.

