11.3.6. Criteria for Endpoints

Primary and major secondary endpoints will be evaluated based on the analyses specified in the efficacy analysis section. The effectiveness of CNTO 1959 treatment in this study will be reached if at least the CNTO 1959 high dose group is shown to be superior to placebo group for the primary efficacy analysis.

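### The 90% power in Section 11.2 holds for 200 mg, but not for 100 mg as the fixed sequence tests it (about 84% to 86%), and the 75 per group said to be required at SD 10 should be 71

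*Protocol*

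**What the plan says.** Section 11.2 names a fixed-sequence procedure starting with 200 mg, then states that the sample size was chosen for "at least 90% power to detect treatment difference between CNTO 1959 groups and placebo for the primary endpoint" at two-sided 0.05. The inputs follow: "Assuming a 5.5 treatment effect for both CNTO 1959 groups and a common standard deviation (SD) of 8.1". The worked result is narrower than the general sentence: "47 subjects per group will provide statistical power of 90% for comparisons of CNTO 1959 200 mg versus placebo". The note under Table 2 gives the method as a two-sample t-test with equal variances.

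The Synopsis repeats the general claim with the word group in the singular and no dose named: "chosen to achieve at least 90% power to detect treatment difference between CNTO 1959 group and placebo for the primary endpoint".

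On the test order, Section 11.3.3 says of 200 mg and then 100 mg: "Only if this test is positive will the low dose group" be compared with placebo. Section 11.3.6 counts the study as successful "if at least the CNTO 1959 high dose group is shown to be superior to placebo group".

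For a larger variance (difference 5.5, SD 10), Section 11.2 says "the required number of patients per group for a 90% power is 75". It explains the planned 50 per group by long-term safety: "an evaluable long-term safety population for CNTO 1959 is considered to have at least 50 patients per group". It states no dropout allowance. Section 11.8 describes the maximum as about 1.5 times the original size.

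**The concern.** Two stated figures do not match the plan's own test.

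**Power for 100 mg.** The general sentence covers both doses, but the supporting calculation treats one comparison as if it stood alone. In this plan 100 mg never stands alone. It is declared superior only if both its own test and the 200 mg test are significant, so its power must be lower than the stand-alone figure. A reader who takes at least 90% to apply to both doses would expect a truly effective 100 mg to be missed in at most 10% of trials. Section 3.2 says the two doses are there to find the appropriate dose level, so a failed or untested 100 mg comparison could be over-read as lack of effect.

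**The 75 per group.** It is presented as a computed requirement and supports the maximum of 225. A number given as required for a stated difference, SD and power should follow from the method used in the same section.

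**Working it through.** **Inputs.** Difference 5.5 for both doses, SD 8.1, two-sided 0.05, two-sample equal-variance t-test, 47 per group, planned 50 per group, and the second scenario of 5.5 with SD 10 (all Section 11.2). Allocation 1:1:1 with one shared placebo arm (Section 5). 100 mg tested only after a significant 200 mg result (Section 11.3.3).

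**Step 1: reproduce the plan's figure.** Power is P(|T| > t(0.975, 2n−2)), where T is noncentral t with noncentrality difference / (SD × √(2/n)).

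| n per group | Noncentrality (5.5, SD 8.1) | Power, one dose alone |
|---|---|---|
| 46 | – | 89.6% |
| 47 | 5.5/(8.1 × √(2/47)) = 3.29 | 90.3% |
| 50 | 5.5/(8.1 × √(2/50)) = 3.40 | 91.9% |

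So 47 is the smallest n that gives 90%, as stated. All nine entries of Table 2 also reproduce to within 1 percentage point (for example 82.1% against 82%, 76.0% against 75%, 87.4% against 87%). This is the plan's own method.

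**Step 2: 100 mg behind the gate.** The quantity is P(200 mg significant and 100 mg significant). The two statistics share the placebo arm, so with equal group sizes their correlation is about 0.5. Three arms were simulated with effects 5.5 and 5.5 and SD 8.1, 1,000,000 trials per setting.

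| n per group | Separate two-sample t-tests | Variance pooled over three arms | Bivariate normal check |
|---|---|---|---|
| 47 | 83.7% | 84.0% | 84.6% |
| 50 | 86.3% | 86.5% | 87.1% |
| 55 | 89.8% | 90.1% | – |
| 56 | 90.5% | 90.7% | – |

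A true 5.5-point effect at 100 mg would therefore go undeclared in about 16% of trials at 47 per group (100 − 83.7) and 14% at 50 (100 − 86.3). On this basis 90% for 100 mg needs about 55 to 56 per group.

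**Step 3: the 75 at SD 10.** Same t-test, difference 5.5.

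| n per group | Power |
|---|---|
| 70 | 89.8% |
| 71 | 90.2% |
| 75 | 91.7% |

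The required number is 71. The normal approximation gives 70, alpha 0.025 gives 84, and one-sided 0.05 gives 58. None gives 75. Among the values of n, 75 is the smallest that reaches 90% only if the SD lies between 10.25 and 10.32. A 5% dropout allowance would explain it (71/0.95 = 74.7), and the same allowance would turn 47 into 50 (47/0.95 = 49.5), but the section states none and gives long-term safety as its reason for the 50. The 75 also equals 1.5 × 50.

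**Step 4: how far baseline adjustment could move Step 2.** Table 1 gives an ANCOVA standard error of 2.061 with 24 and 25 subjects. Then 2.061/√(1/24 + 1/25) = 2.061/0.2858 = 7.21. This is an upper bound on the residual SD, because baseline imbalance also enters that standard error. At SD 7.21 the gated power for 100 mg is 92.1% at 47 per group and 93.8% at 50.

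**The case against.** The strongest reply is that power is ordinarily quoted per comparison, and read that way the general sentence is true for each dose (91.9% at the planned 50). The next paragraph ties the worked 90% to 200 mg by name, and Section 11.3.6 makes 200 mg alone decisive, so powering on 200 mg is coherent. All of that stands, and it is why the design is not in question. It does not rescue the plural sentence: that sentence comes straight after the fixed sequence is named, and under that sequence 100 mg has no stand-alone test.

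A second reply is that 84% and 86% are not the power of the trial that will be run. The primary model adjusts for baseline, and Step 4 shows this could bring 100 mg above 90%. The sample size may also rise to 75 per group. A normal-approximation simulation assumed 20 per group at the interim, a promising zone of conditional power from 42% to 90%, and the cap of 75. It gave gated power of about 90% with no futility stop, and about 88%, 87% and 84% with assumed futility bounds of 5%, 10% and 20%. The protocol leaves the futility bound to a separate document, so the actual figure cannot be fixed from it. This stands as a limit on how the 84% and 86% may be used: they must carry their basis. But Section 11.2 itself computes with SD 8.1, no covariate and fixed n, and on that basis its general claim does not cover the gated test.

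On the 75, the reply is that it is conservative and only motivates a cap. That is correct as to consequence. The number still is not the one required.

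**Conclusion.** Both points hold, at low severity. On the protocol's own inputs (5.5 for both doses, SD 8.1, unadjusted t-test, fixed n), the at-least-90% statement is right for 200 mg and for either dose tested alone. For 100 mg as the plan tests it, the figure is about 84% at 47 per group and 86% at 50. Baseline adjustment may raise this, re-estimation may raise it, and a futility stop would pull it down, but Section 11.2 calculates none of these. The Synopsis sentence is only unclear, because it names no dose.

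The 75 per group at SD 10 is 4 above the 71 that the same test requires, and it gives 91.7% instead of 90%. The discrepancy is on the safe side. Type I error, enrolment, the interim rule and the analysis are unaffected by either point.

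**What to change.** Wording only.

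1. In Section 11.2, limit the general power sentence to 200 mg versus placebo (90% at 47 per group, 92% at 50), and name 200 mg in the matching Synopsis sentence.
2. Add a sentence such as: *Because 100 mg is tested only if 200 mg is significant, the power to declare 100 mg superior with the same effect is about 84% (47 per group) or 86% (50 per group), for a fixed design, an unadjusted t-test and SD 8.1.* Quote a higher figure only with its basis named, whether baseline adjustment or re-estimation.
3. For the SD 10 scenario, give 71 per group as the number required for 90% power and describe 75 as the cap (1.5 × 50), which gives about 92%. Alternatively, keep 75 and state the dropout allowance that leads to it. The cap itself should stay at 75, because Section 11.8 rests its type I error argument partly on that ratio.

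The only cost is that the stated power for 100 mg becomes less favourable.

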11.3. Efficacy Analysis

11.3.1. Analysis Data Set

For the efficacy analyses, all randomized subjects will be included. Subjects will be analyzed according to the treatment group to which they were randomized, regardless of the treatment they actually received.

Summaries and analyses of most of the secondary endpoints will be based on the subset of subjects with evaluable measurements according to their randomized treatment group. For subjects randomized to placebo, only subjects crossed over to receive CNTO 1959 at Week 16 will also be included in the efficacy summaries after Week 16 (from Week 20).

11.3.2. Efficacy Definitions

Treatment Failure: Subjects who discontinue study treatment due to lack of efficacy or an AE of worsening of Palmoplantar Pustulosis, or who started a protocol-prohibited medication/therapy during the study that could improve Palmoplantar Pustulosis are considered treatment failures. The treatment failure rules and handlings of efficacy data for patients with treatment failure will be documented in detail in the SAP.

PPPASI 50 Responders: Subjects with $\geq 50\%$ improvement in PPPASI from baseline will be considered PPPASI 50 responders.

PPPASI 75 Responders: Subjects with $\geq 75\%$ improvement in PPPASI from baseline will be considered PPPASI 75 responders.

PPPASI 90 Responders: Subjects with $\geq 90\%$ improvement in PPPASI from baseline will be considered PPPASI 90 responders.

PPPASI 100 Responders: Subjects with 100% improvement in PPPASI from baseline will be considered PPPASI100 responders (ie, PPPASI score = 0).

11.3.3. Primary Analysis

Primary endpoint of this study is change from baseline in PPPASI total score at Week 16. In the primary efficacy analyses, data from all randomized subjects will be analyzed according to their assigned treatment group. In this primary analysis, the change from baseline in PPPASI total score through Week 16 will be analyzed using an MMRM with treatment (CNTO 1959 high dose, CNTO 1959 low dose, or placebo), smoking status (smoking or non-smoking), week (2, 4, 8, 12, 16), and treatment-by-week interaction as fixed effects and baseline PPPASI score as a covariate. Un-imputed data will be used for MMRM analyses and data is assumed to be missing at random (MAR). An unstructured covariance structure will be used to model the within-patient error. If the model with unstructured covariance structure doesn't converge, the compound symmetry structure will be used. Based on the MMRM model described above, treatment effects of CNTO 1959 groups versus placebo group at Week 16 will be estimated based on least-square (LS) means of the differences. The p-values for the LS mean differences along with the 2-sided 95% CIs will be presented.

Sensitivity analyses for primary endpoint (change from baseline in PPPASI total score at Week 16) will be performed using an ANCOVA model with treatment (CNTO 1959 high dose, CNTO 1959 low dose, or placebo) and smoking status (smoking or non-smoking) as factors and baseline PPPASI score as a covariate, based on the data with and without imputation of last observation carry forward (LOCF). The last available post-baseline PPPASI total score will be carried forward to impute the PPPASI total score that are missing after discontinuation of treatment up to Week 16 of the double-blind treatment period.

Furthermore, subgroup analyses will be performed to evaluate consistency of the primary endpoints over demographics and baseline disease characteristics as appropriate. The exploratory analyses for the primary endpoints to evaluate the dose-response may be performed if deemed appropriate. Additional efficacy analyses may also be performed and will be documented in the SAP.

A fixed-sequence testing procedure will be used to control the overall Type I error rate at the 0.05 level for the primary endpoint. Specifically, the high dose group (i.e., CNTO 1959 200 mg) will first be compared with the placebo group at the 2-sided 0.05 level of significance. Only if this test is positive will the low dose group (i.e., CNTO 1959 100 mg) be compared with the placebo dose group at the 2-sided 0.05 level of significance.

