11.3.4. Major Secondary Analyses

Major secondary endpoints of this study are not prospectively powered and all p-values reported for secondary endpoints will not adjust for multiple comparisons. Major secondary analyses are:

- The change from baseline in PPSI through Week 16 will be analyzed using the same MMRM model as described for the primary analysis, except for including the baseline PPSI score, instead of baseline PPPASI score, as the covariate. Treatment effects of CNTO 1959 groups versus placebo group will be estimated based on least-square (LS) means of the differences. The p-values for the LS mean differences along with the 2-sided 95% CIs will be presented. The change from baseline in PPSI through Week 16 will also be summarized by treatment group and week using descriptive statistics.
- The proportion of subjects who achieve a PPPASI-50 at Week 16 will be compared between the CNTO 1959 treatment groups and placebo group using a CMH chi-square test stratified by baseline PPPASI total score (≤ 20 , 21-30, ≥ 31) and smoking status (smoking or non-smoking). The proportion through Week 16 will also be summarized by treatment group and week using frequencies and percentages with 95% CI.

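### The primary MMRM fits one baseline PPPASI slope for all weeks; if the true slope grows over visits, the Week 16 standard error is wider than it need be (0% to about 13%)

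*Protocol*

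**What the plan says.** Protocol Section 11.3.3 and the efficacy part of the synopsis write out the primary model. Besides treatment and smoking status it has "week (2, 4, 8, 12, 16), and treatment-by-week interaction as fixed effects and baseline PPPASI score as a covariate". No product of baseline and week is listed. On the covariance, "An unstructured covariance structure will be used to model the within-patient error"; if that model does not converge, "the compound symmetry structure will be used". The primary result is the Week 16 LS mean difference of each dose from placebo.

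Section 11.3.4 carries the form over to PPSI, a major secondary endpoint: "the same MMRM model as described for the primary analysis, except for including the baseline PPSI score" in place of baseline PPPASI.

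One planned analysis does estimate a baseline slope at Week 16 alone. Section 11.3.3 states: "Sensitivity analyses for primary endpoint (change from baseline in PPPASI total score at Week 16) will be performed using an ANCOVA model with treatment", with smoking status and baseline PPPASI also in the model, run with and without LOCF.

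Section 11.2 sets the sample size: "Assuming a 5.5 treatment effect for both CNTO 1959 groups and a common standard deviation (SD) of 8.1", by a two-sample t-test, giving 90% power with 47 per group; 50 per group are planned.

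**The concern.** Only Week 16 is tested, yet the baseline slope used there is shared with Weeks 2, 4, 8 and 12. If change is still small at the early visits, its regression on baseline is probably flatter there. With an unstructured covariance, the shared slope is a weighted average that leans towards the less variable visits. If those are the early ones, the shared slope falls below the Week 16 slope, and the baseline effect left over goes into the Week 16 residual variance.

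Baseline matters at Week 16. In Phase 2 (Table 1) adjustment moved the difference from -3.84 (that is, -10.24 minus -6.40) to -5.65, and the sponsor took its planning effect from the adjusted figure. At stake is precision in the primary test that the collected data could provide.

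**Working it through.** **1. The plan's own figure.** For a difference of 5.5, SD 8.1, 47 per group and two-sided 0.05, the noncentrality is 5.5 / (8.1 × √(2/47)) = 3.29 on 92 df. Power is 90.3%, which agrees with the stated 90%. Every cell of Table 2 reproduces within one percentage point. The Table 1 interval (-9.80, -1.50) and p = 0.009 also reproduce.

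**2. How much baseline explains at Week 16.** Inputs from Table 1: n = 24 and 25, SDs 7.545 and 8.072, raw difference -3.84, adjusted difference -5.65, SE 2.061.
- Within-group sum of squares: 23 × 7.545² + 24 × 8.072² = 2873. Pooled SD = √(2873/47) = 7.82.
- Ignoring baseline imbalance: residual SD = 2.061 / √(1/24 + 1/25) = 7.21, so R² = 1 - (7.21/7.82)² = 0.15.
- Allowing for imbalance: let Q be the sum of squares explained by baseline. The shift of 1.81 equals slope × imbalance, so SE² = [(2873 - Q)/46] × [1/24 + 1/25 + 1.81²/Q]. Solving gives Q = 625, residual SD 6.99, R² = 0.217 and r of about -0.47.

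**3. Cost of a shared slope.** Let k be the shared slope divided by the Week 16 slope. With complete data the Week 16 SE, relative to a model with baseline-by-week, is

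ratio = √(1 + (1 - k)² × R²/(1 - R²)).

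For R² = 0.217 the last factor is 0.278, so k = 1 gives 1.00, k = 0.5 gives 1.034, k = 1/3 gives 1.06, and k = 0 (no effective adjustment) gives 1.13. For R² = 0.15, k = 0 gives 1.085.

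**4. What k might be.** The protocol does not say, so slope profiles were assumed. Each was combined with flat or rising SDs and several exchangeable and autoregressive correlations. Under GLS, k = 1'S⁻¹β / 1'S⁻¹1, where β is the vector of weekly slopes relative to Week 16 and S is the visit covariance.

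| Slope at Weeks 2, 4, 8, 12, 16 relative to Week 16 | Widening, R² 0.217: median (range) | Widening, R² 0.15: median |
|---|---|---|
| 1, 1, 1, 1, 1 | 0% | 0% |
| 0.6, 0.7, 0.8, 0.9, 1 | 2% (0.5–4) | 1% |
| 0.3, 0.45, 0.65, 0.85, 1 | 6% (1.5–13) | 4% |
| 0.1, 0.25, 0.5, 0.8, 1 | 10% (3–21) | 7% |
| 0, 0.1, 0.4, 0.7, 1 | 12% (3.5–25) | 8% |

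With flat SDs and exchangeable correlation, k is the plain mean of the slopes. For the third row that is 0.65, and the ratio is √(1 + 0.35² × 0.278) = 1.017, so flat variability gives small losses. Values above 13% need k below zero, where the shared slope has the opposite sign to the Week 16 slope.

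**5. Simulation.** 3 × 50 subjects, 3,000 runs per profile, SDs rising over visits, autoregressive correlation, true difference 5.5:

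| Profile | k | SE ratio | Type I error, shared slope | Power, shared slope | Power, slope by week |
|---|---|---|---|---|---|
| constant | 1.00 | 1.00 | 0.048 | 0.969 | 0.968 |
| mild | 0.58 | 1.02 | 0.052 | 0.957 | 0.963 |
| moderate | 0.28 | 1.07 | 0.043 | 0.948 | 0.968 |
| steep | 0.09 | 1.11 | 0.057 | 0.921 | 0.964 |

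A separate simulation with stratified blocks (baseline SD about 9 and residual SD rising from 3.5 to 7.0, both assumed) gave 6% to 12.5% with rising SD, 1% to 3% with flat SD, and no loss with a constant slope.

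**6. Power against the plan.** Take raw SD 8.1 and R² = 0.217, so the adjusted SD is 8.1 × √(1 - 0.217) = 7.17. Power at 50 per group is 96.7% with full adjustment, 94.8% at +6% and 92.4% at +12%. With no baseline adjustment at all it is 92.0% at 50 per group and 90.3% at 47.

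**The case against.** The strongest reply is that nothing here is shown to go wrong. Table 1 reports Week 16 only. It supports a baseline relation at that visit and says nothing on whether the slope differs at Week 2. The rising slopes and SDs are assumptions, and R² is back-solved from 49 subjects. All of this stands, and it is why the size is given as a range that starts at zero.

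The Phase 2 shift from -3.84 to -5.65 also mixes a slope with a chance imbalance. Section 11.2 attributes that imbalance to baseline PPPASI not having been a stratification factor, and in this trial it is one. That stands too: a shift of that size is much less likely here. Stratified allocation does not, however, take baseline variance out of the SE that the model reports.

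The ANCOVA planned as a sensitivity analysis fits a Week 16 slope and would show a material discrepancy. It limits the consequence, but the primary test still rests on the MMRM.

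Finally, a shared-slope MMRM is a valid prespecified analysis of a randomized comparison, and Section 11 describes itself as general, with details left to the SAP. It is valid, but Section 11.3.3 lists the model terms explicitly, so the shared slope is a stated choice.

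**Conclusion.** The point holds as a possible and avoidable loss of precision. With R² of 0.15 to 0.22 at Week 16, the SE could be wider by 0% if the slope is constant and about 2% if it grows mildly. With moderate to steep growth, typically with SD rising over visits, the widening is about 6% to 12% at the upper R² and about 4% to 8% at the lower. About 13% corresponds to no effective baseline adjustment. Confidence in the mechanism is good; confidence in the size is limited, because no weekly slopes, SDs or correlations before Week 16 are reported. PPSI shares the model form, but its loss was not quantified.

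Stronger readings that the documents do not support:
- A reader might infer that Week 16 is in fact under-adjusted by 6% to 12%. That needs slope growth which the protocol neither reports nor rules out.
- A reader might infer that the trial is underpowered. The sample size used SD 8.1, at the level of the raw Phase 2 SDs, and claimed no gain from baseline. While the shared slope lies between zero and the Week 16 slope, the model does no worse than that calculation. Only the extreme corner of the assumed covariances, with k below zero, falls outside this, and nothing in the protocol points there.
- A reader might infer false-positive risk. Simulated type I error was 0.043 to 0.057.
- A reader might infer that the missing-at-random assumption is weakened. The protocol gives no dropout rate and no link between dropout and baseline, so that is not claimed.

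**What to change.** Add baseline PPPASI-by-week to the primary MMRM and baseline PPSI-by-week to the PPSI MMRM, and keep every other term. With complete data the Week 16 contrast then has essentially the precision of a Week 16 ANCOVA. The observed-case sensitivity ANCOVA would also adjust for baseline in the same way as the primary model, so a difference between the two would speak more directly to missing data.

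The cost is 4 degrees of freedom per model (five weeks, four extra slopes) and wording changes in the synopsis, Sections 11.3.3 and 11.3.4, and the SAP. No new data are needed. In the simulations the extra term cost nothing visible when the slope was constant (power 0.968 against 0.969), so this is close to a free improvement.
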